## **19.2 Data Safety Monitoring**

The Hackensack Meridian Health Data and Safety Monitoring Board (DSMB) will be responsible for the data and safety monitoring of this trial. As this study is an investigator initiated feasibility study utilizing a non-FDA approved supplement for which the PI holds the IND it is considered a moderate risk study which requires real-time monitoring by the PI and study team and reviewed monthly by the HMH DSMB.

The Principal Investigator and the Co-Investigators will review the data including safety monitoring at their weekly institution-based meetings and on monthly teleconferences. All Severe Adverse Events (SAEs) are required to be reported to the IRB. Based on SAEs, the IRB retains the authority to suspend further accrual pending more detailed reporting and/or modifications to further reduce risk and maximize the safety of participants. Progress on the trial will be reviewed by the HMH DSMB monthly from the time the first participant is enrolled on the study. Results of the DSMB meetings will be forwarded to the IRB with recommendations regarding need for study closure. DSMB recommendations should be based not only on results for the trial being monitored as well as on data available to the DSMB from other studies. It is the responsibility of the PI to ensure that the DSMB is kept apprised of non-confidential results from related studies that become available. It is the responsibility of the DSMB to determine the extent to which this information is relevant to its decisions related to the specific trial being monitored. A written copy of the DSMB recommendations will be given to the trial PI and the IRB. If the DSMB recommends a study change for participant safety or efficacy reasons, the trial PI must act to implement the change as expeditiously as possible. If a recommendation is made to change a trial for reasons other than patient safety or efficacy, the DSMB will provide an adequate rationale for its decision. Authority to close a trial for safety reasons lies with the IRB, with the above described input from DSMB.

## **19.3 End of Study**

The End of Study will occur when all participants have completed the 6 month follow-up period (i.e., when the last patient has expired, been followed for 6 months after last dose of study drug, been lost to follow-up, or has withdrawn consent, whichever occurs first). At the 6 month point, one of the study physicians or the RC will call the subject with a quick phone survey, captured in REDCap.

## **20.0 Ethical considerations and Trial Administration**

### **20.1 Institutional Review Board (IRB) Review**

The final study protocol, ICF, and surveys including data collection tools will be approved by the Hackensack Meridian Health Institutional Review Board (IRB). Approval will be received in writing before initiation of the study.

Any changes to the study design will be formally documented in protocol amendments and will be approved by the IRB prior to implementation.

### **20.2 Subject Confidentiality**

The patient collected data, and all analysis of the data will adhere to HIPAA & institutional patient confidentiality requirements as described above.

More specifically, a coding system will be used for which a unique identifier (study ID number) will be assigned to each patient name and contact details. Only the study number will be included in the data collection tool, data analysis software and potential publications. The list with the direct identifiers (for the purposes of linking data with the samples and keeping track of patients) will be stored separately in a secure server at each site.

Analytical datasets will be stored on secure servers that also limit access to the investigator team. Should results of the study be published or reported, individual names or other identifying information will not be used.

### **20.3 Data Storage/Security**

All data will be stored on a Hackensack Meridian Health password protected computer only accessible by the investigator team.

Electronic data will be managed using a secure, web-based system that has user-level access control. Analytical datasets will be stored on secure servers that also limit access to the investigator team.

### **20.4 Retention of Records**

Records will be retained in accordance with regulatory, organizational and sponsor requirements, but for no less than six (6) years following the completion of the research. Disposal of records will be done in such a manner that no identifying information can be linked to research data.

## Appendix A: Inclusion / Exclusion Eligibility Survey

Confidential

Page 1

## Inclusion/Exclusion Eligibility Survey

Please complete the survey below.

Thank you!

---

1. Are you a team member at Hackensack Meridian Health?  Yes  No

---

2. Are you age 18 or over?  Yes  No

---

3. Have you tested positive for coronavirus (COVID-19) via PCR test? (Note: home test or other rapid test MUST be confirmed by a PCR test)  Yes  No

---

4. On what date were you diagnosed with Covid-19 via PCR test? \_\_\_\_\_

---

5. Have you been experiencing symptom(s) related to covid-19 for more than 12 weeks after initial infection?  Yes  No

---

6. Which of the ongoing covid-19 symptoms have you been experiencing? (please check all that apply)  Respiratory symptoms (shortness of breath and/or cough)  Fatigue  Loss of taste  Loss of smell

---

7. Were any of these symptoms present before your covid-19 infection?  Yes  No

---

8. Where you ever hospitalized for covid-19?  Yes  No

---

9. Did you require supplemental oxygen for covid-19?  Yes  No

---

10. Do you have a known soy allergy?  Yes  No

---

11. Do you have a known allergy to fish?  Yes  No

---

12. Are you able to take an online survey every other week (bi-weekly) for the study?  Yes  No

---

13. Are you able to take your own blood pressure and record it in bi-weekly online survey?  Yes  No

---

14. If you qualify, are you willing to participate in this 12-week study and be assigned to either intervention or placebo arm? This means you will be assigned to either take the omega-3 supplement or a placebo (pill with soybean oil in it).  Yes  No

Confidential

Confidential

Page 2

15. Are you currently taking an omega-3 supplement or other high-dose supplement (over 2,000 IU) with potential for aiding recovery of long covid syndrome (e.g. zinc, Vit C, Elderberry)?

 Yes No

16. Are you able to take/swallow six mini-pills daily?

 Yes No I don't know

17. Are you able and willing to give a spot blood sample (2 drops) at the beginning (baseline) and end of the study?

 Yes No

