## **3.0 Background**

### **Supplement Interventions for Recovery of Post-Acute Sequelae of Covid-19 (Long Covid Syndrome)**

Since COVID-19 launched a worldwide pandemic in December 2019, non-prescription interventions have been and continue to be explored to limit the effects of the virus. As COVID-19 is novel, few studies on nutritional interventions have been completed. Much of the literature focuses on the breadth of possible or potential nutrition-based measures, including dietary protein, omega-3 fatty acids, vitamin A, vitamin D, vitamin E, vitamin B1, vitamin B6, vitamin B12, vitamin C, iron, zinc, and selenium [1]. Numerous analyses focus on Vitamin D, Vitamin C, and zinc [2,3,4]. Vit. D has been found to inhibit viral replication and have anti-inflammatory and immune-modulating effects, but as with other supplements used for prophylaxis, controlled trials specific to COVID-19 are needed [2, 4]. One longitudinal study in the UK, announced in June 2020, is examining Vit D status of 12,000 adults over the 2020-21 winter and will include a sub-analysis to determine if minority ethnic groups are more adversely affected [4]. Another study suggests that 2,000-5,000 IU of Vitamin D daily for older adults with Parkinson's disease (PD) may slow PD progression and have a protective effect against COVID-19 [5]. All of these studies, however, address active covid-19 infection, not the potentially long recovery period afterwards that is gaining worldwide attention.

The NIH has termed this symptomatic recovery period "Post-acute Sequelae of Covid-19" or "Long Covid Syndrome." To address this, NIH held its first workshop dedicated to the topic in December 2020 [6]. From severe hospitalized cases to mild outpatient cases, the road to recovery is complex and not yet well understood, though a few studies published thus far provide insights and researchers are beginning to study what interventions may be beneficial.

These patients, also known as long-haulers or those with post covid syndrome, have been shown to suffer from after-effects for 12+ weeks after contracting the virus. Effects may be most severe in patients with underlying lung disease such as asthma and/or who had a more severe form of covid-19, including those hospitalized. However, even

those having initially recovered from a mild case of the virus report long-term effects [7].

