## 10.0 Inclusion and Exclusion Criteria

### Inclusion Criteria

- Team member at Hackensack Meridian Health
- Age: 18+
- Willing to provide informed consent
- Formal diagnosis of COVID-19 via PCR test (if home test was done, team member must confirm via PCR test)
- Outpatient treatment only for covid-19; no hospitalization (most team members will be vaccinated and may likely have milder case)
- Must be experiencing 1+ ongoing covid-19 symptom being measured in this study (respiratory symptoms (shortness of breath, cough), fatigue, loss of taste, loss of smell)
- Symptom(s) have persisted for more than 12 weeks after initial infection

- Symptom(s) coincided with covid-19 infection and were not present prior to covid-19 infection
- Does not have soy allergy
- Does not have allergy to fish
- Able to participate in bi-weekly surveys in REDCap
- Able to take own blood pressure and record it in bi-weekly REDCap survey
- Willing to participate in 12-week study and be assigned to either intervention or placebo arm
- Not currently taking an omega-3 supplement or other high-dose supplement (over 2,000 IU) with potential for aiding recovery of long covid syndrome (e.g. zinc, Vit C, Elderberry).
- Able to take/swallow six mini-pills daily
- Able and willing to give a spot blood sample (2 drops) at baseline and end of study.

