### **Exclusion Criteria**

- Not a Team Member at Hackensack Meridian Health
- Not age 18+
- Unwilling to provide informed consent/ declined to take part
- No formal diagnosis of COVID-19 via PCR test (if home test was done, team member must confirm via PCR test)
- Were hospitalized for treatment of covid-19
- Not experiencing 1+ ongoing covid-19 symptom being measured in this study (respiratory symptoms (shortness of breath, cough), fatigue, loss of taste, loss of smell)
- Symptom(s) have persisted for more than 12 weeks after initial infection
- Symptom(s) did not coincide with covid-19 infection and were present prior to covid-19 infection
- Does have soy allergy
- Does have allergy to fish
- Not able to participate in bi-weekly surveys in REDCap
- Not able to take own blood pressure and record it in bi-weekly REDCap survey
- Not willing to participate in 12-week study and be assigned to either intervention or placebo arm
- Currently taking an omega-3 supplement or other high-dose supplement (over 2,000 IU) with potential for aiding recovery of long covid syndrome (e.g. zinc, Vit C, Elderberry).
- Unable to take/swallow six mini-pills daily
- Not able and not willing to give a spot blood sample (2 drops) at baseline and end of study.

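### The eligibility survey does not test onset, prior presence and 12-week duration symptom by symptom, so non-qualifying symptoms can enter the symptom comparison

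*Combined protocol and SAP*

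**What the plan says.** Section 6.2 (steps 1 and 2) and Section 13.0 make the REDCap eligibility survey the step that decides whether the inclusion criteria are met. No clinician check of symptoms is described.

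The inclusion list in Section 10.0 puts the symptom conditions in separate bullets:
- Presence: "Must be experiencing 1+ ongoing covid-19 symptom being measured in this study". The measured symptoms are respiratory symptoms, fatigue, loss of taste and loss of smell.
- Duration: more than 12 weeks after the initial infection.
- Onset: "Symptom(s) coincided with covid-19 infection and were not present prior to covid-19 infection".

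The exclusion list gives the onset condition as "Symptom(s) did not coincide with covid-19 infection and were present prior to covid-19 infection". It also repeats the 12-week line in the same direction as the inclusion list.

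Appendix A turns this into four items:
- Item 4: "On what date were you diagnosed with Covid-19 via PCR test"
- Item 5, yes/no: "Have you been experiencing symptom(s) related to covid-19 for more than 12 weeks after initial infection"
- Item 6, a tick list of the four measured symptoms: "Which of the ongoing covid-19 symptoms have you been experiencing? (please check all that apply"
- Item 7, yes/no: "Were any of these symptoms present before your covid-19 infection"

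Section 4.2 takes the symptom analysis from the bi-weekly survey in Appendix C. Section 17.1 compares the arms on symptom recovery with a chi-square or Fisher's exact test. Neither section says which subjects form the denominator for a given symptom.

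**The concern.** The criteria describe properties of a symptom, but the survey asks about the symptoms as a group. One long-lasting symptom can answer item 5 for all the others, and it need not be one of the four that are measured. Nothing asks when any symptom began, so half of the onset bullet is not screened.

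The secondary objective is to find which symptoms omega-3 affects most, and Section 17.1 calls the comparison on symptom recovery the primary analysis. Both rest on each symptom's analysis set containing people who have that symptom as a lasting consequence of covid. Section 2.0 presents the study as proof of concept for a larger trial, so a diluted symptom estimate would also be a poor basis for planning that trial.

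**Working it through.** The plan states no figure on this point. The check is therefore to run profiles through the survey, see whether later data repair the gap, and then illustrate dilution under stated assumptions.

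**Profiles through items 5 to 7**

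1. *Smell loss for 14 weeks, cough for 3 weeks, neither present before covid.* Item 5 yes, item 6 ticks both, item 7 no: the person passes. Smell loss meets Section 10.0. If smell loss began with the infection, cough began 14 − 3 = 11 weeks later, so cough fails both duration and coincidence of onset. It is still carried into Appendix C.
2. *An unmeasured symptom for more than 12 weeks, fatigue of recent onset, no fatigue before covid.* Item 5 yes, item 6 ticks fatigue, item 7 no: the person passes with no qualifying measured symptom.
3. *Old cough, new smell loss for more than 12 weeks.* Item 5 yes, item 6 ticks both, item 7 yes. If yes on item 7 fails screening, the person is refused. Whether that is correct depends on how the onset bullet is read.

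**Do later data repair it?** Item 4 dates the infection, but there is no symptom-onset date to set against it. Appendix B asks about illnesses, not covid symptoms. Appendix C records when a symptom stopped, that it continues, or that it never occurred. It does not record when a symptom began or whether it preceded covid. Qualification by symptom cannot be rebuilt from these forms.

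**How many subjects could be affected (assumed rates)**

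Let each ticked symptom fail duration or onset with probability u, independently, and let k symptoms be ticked. Among people with at least one qualifying symptom, the share who also carry a non-qualifying one is [1 − (1 − u)^k − u^k] / (1 − u^k).

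| u | k = 2 | k = 3 |
|---|---|---|
| 10% | 0.18/0.99 = 18% | 0.27/0.999 = 27% |
| 20% | 0.32/0.96 = 33% | 0.48/0.992 = 48% |
| 30% | 0.42/0.91 = 46% | 0.63/0.973 = 65% |

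**Dilution (assumed rates)**

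If a share w of a symptom's analysis set does not qualify and treatment has no effect there, the difference between arms becomes (1 − w) times the difference among qualifying subjects. This holds whatever recovery rate the non-qualifying subjects share.

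As an example, take recovery of 30% v 50%, 30% recovery in both arms among non-qualifying subjects, and n = 50 per arm (Section 12.0). The test is two-sided at 0.05; the plan gives 0.05 but not sidedness. With D the diluted difference, p1 and p2 the two rates and p̄ their mean:

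power = Φ{ [D − 1.96·√(2p̄(1 − p̄)/n)] / √[(p1(1 − p1) + p2(1 − p2))/n] }

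| w | Rates | D | Power |
|---|---|---|---|
| 0 | 30% v 50% | 20 points | 53% |
| 10% | 30% v 48% | 18 points | 45% |
| 20% | 30% v 46% | 16 points | 38% |
| 30% | 30% v 44% | 14 points | 30% |

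With 30% v 60%, power falls from 87% to 79%, 69% and 57%. These figures assume that all 50 subjects per arm have the symptom, which is generous for any single symptom.

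**The case against.** The best defence has four parts.

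- **The onset bullet can be read as applying to the whole set.** Only the presence bullet carries the *1+*. If none of the reported symptoms may pre-date covid, item 7 applies the bullet faithfully. This stands. A reader might infer that people are being wrongly refused, but the documents do not establish that: the wording is ambiguous and Appendix A prints no scoring key. If yes on item 7 were ignored, pre-existing symptoms would enter the analysis instead. Neither reading repairs the pooled duration item or the missing onset question.
- **Items 5 and 6 already refer to covid symptoms.** This limits contamination, because profiles 1 and 2 need the respondent to attribute a recent complaint to covid. But self-attribution is not a question about timing, and a late cough or fatigue is easily put down to a known earlier infection.
- **The arms are randomised and blinded, and the study is declared unpowered.** This also stands. The problem should fall equally on both arms, so an inference of bias between arms is not supported.
- **The loosely worded exclusion admits nobody who fails inclusion.** True: the onset inclusion bullet must still be met. The joining word matters only because no survey item tests that bullet.

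Three further inferences do not hold. Section 3.0 says "Effects may be most severe in patients with underlying lung disease such as asthma", which might suggest that item 7 removes the people most affected. Item 7 asks about symptoms, not diagnoses, and the same sentence goes on to name hospitalised patients, whom Section 10.0 excludes on purpose. Understated enrolment yield is not a named feasibility result: Section 4.1 assigns feasibility to the Appendix D survey, which has no enrolment measure. Combining shortness of breath and cough in item 6 matches the four-symptom definition in Sections 4.2 and 10.0.

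A fair limit on the remedy is that the last dated recovery option in Appendix C is the fourth week after diagnosis. Cleaner analysis sets will not by themselves make recovery during the study measurable. That needs its own correction.

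**Conclusion.** The point holds in this form: the only described screen does not apply the Section 10.0 symptom criteria to each symptom. As written, it admits people with no qualifying measured symptom, and it lets non-qualifying symptoms into a comparison that has no denominator rule. The consequences are ineligible enrolment and a symptom effect diluted toward no difference.

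The size cannot be derived, because the documents give no rates for late-onset, short-duration or pre-existing symptoms. The proportional shrinkage (1 − w) follows by arithmetic once treatment is assumed to have no effect on non-qualifying symptoms. The values of w and u, the independence of symptoms and the recovery rates are all assumptions. Whether item 7 also refuses people who should be eligible stays open until the sponsor states its reading of the onset bullet and how item 7 is scored.

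**What to change.** 1. **Appendix A.** Replace items 5 to 7 with a grid over the measured symptoms: respiratory (which may be split into shortness of breath and cough to match Appendix C), fatigue, taste and smell. For each row ask whether the symptom is present now, began with the covid infection, was present before it, and has lasted more than 12 weeks. Require at least one row to meet the inclusion criteria, and print the scoring rule.
2. **Section 10.0, reading.** State whether the onset bullet applies to each symptom or to all reported symptoms, that is, whether one old symptom beside a new qualifying one disqualifies. The grid supports either reading.
3. **Section 10.0, consistency.** Make the onset exclusion the logical complement of the inclusion bullet (*or* in place of *and*). Reconcile the 12-week line that now stands as both inclusion and exclusion, and reconcile both with the 28-day interval in the Section 1.0 study population. The duration column of the grid should follow what the sponsor confirms.
4. **Sections 4.2 and 17.1.** Restrict each symptom's recovery analysis to subjects whose baseline row for that symptom qualifies, and report the number in each arm.

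The cost is one REDCap grid, about one extra minute per applicant, short text changes that need IRB approval, and slightly smaller analysis sets for each symptom.

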## Appendix B: Demographic/Baseline Survey

Confidential

## Demographic / Baseline Survey - Covid Recovery Study

Page 1

Please complete the survey below.

Thank you!

What is your last name?

---

Please provide your mailing address so that we can mail your kit of supplies for study participation.  
Your supplies will arrive by FedEx, in 2 shipments.

---

What is your first name?

---

What is your gender?

- Female
- Male
- Unknown

What is your race?

- Black or African American
- White
- Asian
- American Indian or Alaska Native
- Other
- Unknown

(choose multiple if needed)

What is your ethnicity?

- Hispanic
- Non-Hispanic
- Unknown

Other race not listed above

---

What is your cell phone number? (This will only be used by the study team to reach you.)

---

What is your work phone number? (This will only be used by the study team to reach you.)

---

What is your age?

---

Has any doctor or other health care provider ever told you that you have any of the following illnesses?  
(please check all that apply)

- Diabetes or high blood sugar
- Hypertension or high blood pressure
- High cholesterol
- Stroke (ischemic or hemorrhage)
- Chronic lung disease such as asthma, emphysema, or chronic bronchitis
- Heart disease
- Cancer (other than skin cancer)
- Depression
- HIV/AIDS
- COPD
- Other

If "other" is checked off, please specify.

---

Confidential

Page 2

Please list any recent (adult) allergies to food, medicine, herbal or environmental items, with the reactions and dates.

---

Do you use tobacco products ( e.g., cigarettes, cigarillos, e-cigs, cigars)?

- Yes, I currently use tobacco products
- No, but I used tobacco products in the past
- No, I have never used tobacco products

---

Have you received the covid-19 vaccine?

- Yes
- No

---

Are you currently experiencing any side effect(s) from the covid-19 vaccine?

- Yes
- No

---

If yes, please describe:

---

## Appendix C: Bi-weekly Symptoms & Quality of Life Post Covid Survey

Confidential

Page 1

## Bi-weekly Symptoms & Quality of Life Post Covid19 Survey

Thank you for agreeing to participate.

Please complete the survey below.

Please feel free to skip any question that makes you feel uncomfortable or just close the survey window if you change your mind and you no longer want to participate to our study.

Thank you for your time.

How was your overall health before you got sick with COVID-19?

- Excellent
- Very good
- Good
- Fair
- Poor

With whom do you live?

- Alone
- With family
- Roommates
- Other
- I do not want to answer this question

Please specify

**Considering the past 14 days, please rate your answers. Should you choose to not answer a question, please leave it blank.**

	Excellent	Very good	Good	Fair	Poor
In general, would you say your health is:					
In general, would you say your quality of life is:					
In general, how would you rate your physical health?					
In general, how would you rate your mental health, including your mood and your ability to think?					
In general, how would you rate your satisfaction with your social activities and relationships?					

Confidential

Page 2

In general, please rate how well you carry out your usual social activities and roles. (This includes activities at home, at work and in your community, and responsibilities as a parent, child, spouse, employee, friend, etc.)

To what extent are you able to carry out your everyday physical activities such as walking, climbing stairs, carrying groceries, or moving a chair?

Completely  
 Mostly  
 Moderately  
 A little  
 Not at all

How often have you been bothered by emotional problems such as feeling anxious, depressed or irritable?

Always  
 Often  
 Sometimes  
 Rarely  
 Never

How would you rate your fatigue on average?

Very Severe  
 Severe  
 Moderate  
 Mild  
 None

**Considering the past 14 days, please rate the amount of difficulty you had when doing the following activities. Should you choose not to answer a question, please leave it blank.**

	No difficulty	A little difficulty	Some difficulty	Much difficulty	I did not do this in the past 7 days
Dressing yourself without help					
Walking 50 steps/paces on flat ground at a normal speed without stopping					
Walking up 20 stairs (2 flights) without stopping					
Preparing meals					
Washing dishes					
Sweeping or mopping					
Making a bed					
Lifting something weighing 10-20 lbs (about 4.5-9kg, like a large bag of groceries)					

Confidential

Page 3

Carrying something weighing 10-20 lbs (about 4.5-9kg, like a large bag of groceries) from one room to another

Walking (faster than your usual speed) for  $\frac{1}{2}$  mile (almost 1 km) without stopping

